8.3.4 Documentation on adverse events

Any AE (not serious or serious), occurring after the subject has provided informed consent specific for this trial before completion of the trial, must be documented on the pages intended for adverse events in the Individual Case Record Form (ICRF).

The non-leading questions to the subjects should be used at each trial visit in order to detect AE. AEs can be also detected if the subjects report on them themselves during visits or between the visits as well as if they are found during examination, by the results of laboratory analyses or other tests. All AEs require proper treatment. Actions taken to cure AE should be documented and related to one of the following categories: "no action taken", "prescription of the drug (accompanying therapy)", or "other treatment". Besides, the actions undertaken in relation to the study drug should be documented and referred to one of the following categories: "no changes", "withdrawal", "dose reduced", "dose increased", "therapy suspended", "action is unknown", and "not applicable". Concomitant therapy, other treatment methods, or changes of the study drug should be determined and documented.

The medical conditions/disorders present before the trial therapy initiation are considered to be AEs unless they get worsened after the inclusion in the trial. Abnormal laboratory or test results are considered to be AEs only if they evoke clinical signs, are clinically significant, or require therapy.

After detection of AE, it should be followed up until its resolution or until it is recognized as permanent. The event outcome should be documented and referred to one of the following categories: "event not resolved/did not change", "health status gets worse", "event resolved/subject recovered", "event improved/subject recovers", "event resolved/subject recovered with complications", "lethal outcome", or "outcome unknown". Evaluation of AE should be performed during each visit (or more frequently, in case of any indications) for any changes in severity, suspected association with the study drug, interventions undertaken for its treatment, and outcome.

AE in the interval between signing of informed consent and administration of the first dose

Any AEs, which occurred in the interval after signing of informed consent specific for this trial and before administration of the first dose, should be documented as screening period events. Moreover, the results of evaluation of the association with the study drug should be documented as follows: "study drug was not administered yet".

AE after the first dose of the study drug

The Investigator should follow up all the AEs occurred since the first intake of the drug and during the trial, till the last visit of the subject when the event outcome is evaluated for the last time with further recording in eCRF.

SAEs not resolved as at the last visit

If SAE is not resolved as at the last visit, the Investigator should follow up the subject till SAE resolution or stabilization/shift to a permanent stage (for SAEs with a suspected relation to the study drugs) or during up to 30 days since the last visit for SAEs without suspected relation to the study drugs.

The Investigator must report on the SAE follow up as per the Reports on SAEs, Section 8.8.5. below.

SAEs registered after the last visit

At the last visit, the Investigator should instruct each subject to report on any new SAEs (outside a follow-up period according to the protocol) which, in the subject's opinion, might be associated with the study drugs. The Investigator must inform recipients on SAR as per the Reports on SAEs, Section 8.3.5. below.

Protocol No. TE_004_ANG_LOZ

Clinically relevant abnormal laboratory results at the last visit

The Investigator must document the clinically significant, abnormal laboratory results revealed at the last visit as AEs even without any relation with the specific study drug.

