4.1.2. Safety parameters

The following parameters will be taken into account for the safety evaluation:

- AEs and/or SAEs rates per trial arms;
- Global tolerance evaluation during the trial by the Investigator and patient;
- Vital signs (heart rate, blood pressure, body temperature, breathing rate);
- ECG parameters;
- Laboratory results.

The AEs will be described according to the scheme given below:

Protocol No. TE_003_ANG_LSP

- AE description;
- AE severity;
- AE duration;
- Relation to the study drug;
- Outcome.

All AEs will be coded according to MedDRA terms.

[figure not shown]

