4.2.3.3 Description of the trial procedures

4.2.3.2.1 Collection of medical history, demographic and anthropometric data

Medical history includes the previous diseases, concomitant chronic conditions, hereditary issues, social habits (smoking, alcohol or drug abuse), allergological anamnesis, previous surgeries or traumas, occupational history, permanent or periodic drug therapy. Regarding the present condition: date and time of the first signs manifestation, diagnostic and treatment procedures by the screening, their efficacy. A contraception method used by the patient is specified; by signing the Informed Consent Form, the patient agrees to use one of the recommended contraception methods (by the protocol) during the trial and 1 month after the trial completion.

Primary documents must contain data on the sex, age, race, and ethnicity of the patient. A height meter is used to measure the patient's height in centimeters, the weighing scales—body weight in kilograms.

The anthropometric examinations will be conducted in accordance with the Health Risk Monitoring (EHRM) Recommendation for indicators, international collaboration, protocol and manual of operations for chronic disease risk factor surveys, 2002 (17).

Height should be measured in all the patients (the causes which make the height measurement impossible include hair-style peculiarities (e.g., mohawk), patient's refusal to take off a headwear (e.g., turban), patient's incapacity to stand, exceedance of the height meter's scale). The height meter is a vertically positioned panel with a centimeter division with a sliding horizontal ruler. A standard error must not exceed 2 mm. The patient will be asked to take off his/her shoes, thick clothes, hairpins, or other hair accessories. The patient must touch a vertical panel with his/her hindhead, back, buttocks, calves, and heels (the toes are stuck together). Upper boundary of the external ear canal must be at the same level with lower boundary of the orbital cavity (the jugal bone). The patient will be asked to look forward. If the patient's height exceeds that of the Investigator, the latter should use a platform. A height meter's ruler is put on the patient's head, the scale's divisions are counted. The height must be recorded while the patient is still standing under the ruler. An error must not exceed 0.5 cm.

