5.1 Inclusion criteria

The patients who meet all the inclusion criteria listed below will be included in the trial:

- 1. The Informed Consent Form voluntarily signed by the patient.
- 2. Men and women at the age of 18 to 45 years old, inclusively.
- 3. A diagnosis of acute, uncomplicated, inflammatory and infectious condition of the pharynx associated with the inflammation and pain in the throat.
- 4. Manifestation of the first signs of acute, uncomplicated, inflammatory and infectious condition of the throat (pharyngitis and/or tonsillitis) not more than 48 hours before the inclusion.
- 5. A baseline total sum of TSS (Tonsillopharyngitis Severity Score) points ≥5.
- 6. Body temperature measured in the axillary cavity is less than 37.5 °C.
- 7. Women with childbearing potential should demonstrate a negative pregnancy test result at screening (except for the women after surgical sterilization or menopause for more than 2 years) and use the established contraception methods for at least 3 months before the initiation of the trial therapy and 1 month after completion of the trial.
- 8. Men should use adequate contraception during the trial, since signing of the Informed Consent Form and till the trial completion, and for 30 days after the trial completion.
- 9. Ability to understand the presented information on the clinical trial, readiness to comply with the protocol, ability to use the study drugs by oneself and evaluate the symptoms according to VAS (visual analogue scale) or other questionnaires according to the protocol.

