8.3 Requirements for reporting, registration, and reporting of AEs and intercurrent diseases

8.3.1 Definitions of adverse events and serious adverse events

Adverse event (AE) is any adverse medical event identified in a patient or a clinical trial patient after the use of the drug, which may or may not have a causal relationship with its usage. Thus, adverse event (AE) can represent any adverse symptom (including laboratory deviation from the norm), complaint, or disease, for which a temporal causal relation cannot be excluded with the application of medicinal (investigational) product, regardless of the presence or absence of such a relation.

Serious adverse event (SAE) represents any event, unfavorable from medical perspective, which with any dose:

- Resulted in death;
- Is life threatening;
- Results in disability/incapacity to work;
- Is a congenital anomaly or development defect;
- Requires hospitalization or its extension;
- significant from medical perspective: a decision whether expedited reports are feasible in other situations (e.g., in case of events important from medical perspective, which not directly life-threatening are

for a patient, do not result in death or hospitalization, but pose the patient to risk, or require intervention to prevent one of the above outcomes) shall be made on the basis of medical and scientific evaluation. Such cases should be usually considered serious adverse events.

Adverse drug reaction (ADR) is any adverse event which might have causal relation to the drug in the opinion of the Investigator or Sponsor (see Section 8.3.3 below).

An unexpected adverse reaction is defined as an adverse drug reaction, the nature or severity of which is not consistent with the Reference Safety Information (e.g., SmPC, Investigator's Brochure). The term "severity" is used to describe the intensity of a specific event. This term should be distinguished from the term "serious". Reports which add significant information on specificity, increase in incidence, or severity of the known, already documented serious adverse reactions, constitute the unforeseen events.

Information about side effects already known for this study drug is available in the Investigator's Brochure. This information will be included into Patient Information Sheet, and it should be discussed with the trial subjects.

More details are given in Brief Reference Manual for filling in the Serious Adverse Event Report Form (to be provided by the Sponsor).

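### Protocol 8.3.4 inverts the rule for pre-existing conditions, so sites have opposing instructions on what to record as an adverse event

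*Protocol*

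**What the plan says.** The sentence at issue is in Protocol Section 8.3.4. It says that conditions or disorders that predate trial therapy "are considered to be AEs unless they get worsened after the inclusion in the trial". The sentence after it sets a restrictive rule for laboratory findings: "Abnormal laboratory or test results are considered to be AEs only if they evoke clinical signs, are clinically significant, or require therapy".

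Three other places in the protocol bear on the same question:

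- Section 8.3.1 gives the definition: "Adverse event (AE) is any adverse medical event identified in a patient or a clinical trial patient after the use of the drug".
- Section 8.3.4 opens by fixing what goes on the AE pages: "Any AE (not serious or serious), occurring after the subject has provided informed consent specific for this trial before completion of the trial".
- Section 4.2.3.2.1 gives existing illness its own place: "Medical history includes the previous diseases, concomitant chronic conditions".

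Safety depends on these records. Section 4.1.2 lists "AEs and/or SAEs rates per trial arms" among five safety parameters, Section 3.2 makes the between-arm comparison of AE rates a secondary goal, and Protocol 9.1.4 and SAP 4.1.4 both plan a between-arm test of AE incidence. The SAP contains no rule for conditions already present at baseline, and its Introduction says that it changes nothing relative to the protocol.

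**The concern.** Under the usual treatment-emergent logic, a stable baseline condition is history and a worsening is an event. The 8.3.4 sentence says the reverse. If a site follows it, two things happen to the AE data. Background illness enters both arms, which dilutes any difference between them. Worsening under treatment, which is where harm could show, is exempted.

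The second effect matters for a topical throat product. Protocol Section 2.1.1 lists difficulty swallowing and mouth sores among the undesirable effects of Angal S, and difficulty in swallowing is also an item of the TSS scored at baseline. If the spray aggravated swallowing in a patient who already had that symptom, this would be a pre-existing condition made worse, which is exactly the case the sentence exempts.

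The trial is open-label with up to 20 sites. When two instructions conflict, the choice falls to investigators who know the assigned drug.

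**Working it through.** No arithmetic applies: the point depends on no sample size, error rate or event count. The check is to read the rules side by side.

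**Step 1. What each rule implies for a condition present before therapy.**

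| Course after inclusion | 8.3.4 sentence, read literally | 8.3.1 and the opening of 8.3.4 |
|---|---|---|
| Stable or improving | AE | Not an AE: nothing new occurred after consent or after use of the drug |
| Worsening | Not an AE | AE: the worsening is an adverse change after use of the drug |

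The two columns disagree in both rows, so this is a full inversion and not a difference at the margin.

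**Step 2. Which column fits the rest of the section.** The laboratory rule next to the sentence is restrictive: a finding counts only if a condition is met. The pre-existing-condition rule is inclusive with an exception. Replacing 'unless' with 'only if' would bring it into line with the laboratory rule, with 8.3.1 and with the recording window. That suggests a wording or translation slip, but nothing in the documents confirms it.

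**Step 3. Who is covered.** Inclusion criterion 3 requires "A diagnosis of acute, uncomplicated, inflammatory and infectious condition of the pharynx associated with the inflammation and pain in the throat". Every enrolled patient therefore has at least one condition present before therapy. Taken alone and literally, the sentence makes the pharyngitis itself an AE in every patient in whom it does not worsen.

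**Step 4. Whether anything restates the rule correctly.** Nothing does. SAP 2.3, 4.1.1 and 4.1.4 describe how AEs are classified and compared but not how pre-existing conditions are handled.

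**Step 5. What limits the effect.**

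- Stable history has its own place: medical history (Protocol 4.2.3.2.1) and SAP Table 15, concomitant diseases.
- The titles of SAP Tables 21 and 22 confine them to events after the start of therapy. Table 23, which compares arms and carries a p column, has no such limit in its title.
- Deterioration of the index disease can trigger an unscheduled visit, at which AE evaluation is mandatory (Protocol 4.2.4.5).
- Serious events must be reported within 24 hours (Protocol 8.3.5), which gives serious worsening a separate route.

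**Step 6. What stays unresolved.** Protocol 4.2.4.5 names deterioration of the index disease and AEs as separate reasons for a visit. Section 5.3.1 likewise lists a negative disease course with secondary infection (item 1) apart from a clinically significant AE (item 7). The documents do not say whether a worsening pharyngitis is an AE, a treatment failure or both.

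**The case against.** The strongest reply is that no experienced investigator would act on the sentence. The definition in 8.3.1 comes first and is clear. Non-leading AE questions are asked at every visit. The patient diary (Appendix 3) tells patients to call if they get worse. Serious events have their own reporting rule, and chronic illness is recorded as history. On this view the sentence is a slip that practice would override. The SAP also treats safety variables as of research interest and bases the non-inferiority conclusion on the primary parameter alone (SAP Section 4).

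Much of this stands. A reader might infer that every worsening would be lost and every stable condition counted. The documents do not support that, because the provisions in Step 5 point sites the other way. A reader might also infer an AE rate near 100% in both arms, since every patient has pharyngitis at baseline. That follows only if the sentence is applied alone and against the opening of its own section, so it shows how far the wording is off and is not a forecast.

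The reply does not remove the conflict. The sentence is operative text in the section that tells sites what to document, and it is the only rule on pre-existing conditions in either document. Table titles cannot restore worsening that was never entered.

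**Conclusion.** The rule is wrong as written. It contradicts Section 8.3.1 and the opening of Section 8.3.4, and the SAP does not correct it. The consequence is conflicting instructions at data capture, with the between-arm AE comparison exposed. If all sites followed the literal wording, the comparison would be pushed towards no difference. If sites or investigators differed in what they followed, the direction could not be predicted.

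No numerical size can be derived. The documents give no prevalence of chronic conditions in this population (ages 18 to 45, with many chronic diseases excluded), no expected AE rate, and no indication of how sites would resolve the conflict. Nor do they rank AE incidence as the main safety outcome: Protocol 4.1.2 and 8.1 list five parameters without order.

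The primary endpoint, its analysis and the sample size are untouched. The sentence should be corrected because the AE comparison is a stated goal, but it does not put the primary conclusion at risk.

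**What to change.** 1. Reword the sentence in Protocol 8.3.4 to: *Conditions present before the start of trial therapy are considered AEs only if they worsen after inclusion in the trial.* Keep the existing instruction that events between consent and first dose are recorded as screening-period events, and cross-refer to it.
2. State explicitly whether deterioration of the index pharyngeal disease is recorded as an AE, and reconcile this with Protocol 4.2.4.5, where the two are listed separately. The rewording alone does not settle this.
3. Repeat the rule in SAP 4.1.4, and give Table 23 the same after-start-of-therapy limit as Tables 21 and 22.
4. Notify sites.

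The text change is small: one corrected sentence, one clarification and matching SAP wording. The protocol part must go through the approval procedure in Protocol 11.2. If patients have already been treated under the current wording, AE entries should also be checked against medical history and unscheduled-visit records. Worsening that was never written down may not be recoverable.

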8.3.5 Reports on SAEs

The Investigator must immediately (not later than 24 hours since the receipt of data on SAEs) report any SAEs even in case the Investigator considers these SAEs not related to the study drugs.

The Investigator must use Novartis Serious Adverse Event Report Form to report on SAE for initial or subsequent reporting. The form should be forwarded by fax or email to LPPV with a copy to a manager responsible for the trial (Sponsor/CRO) using the contact information given in a table below.

The Investigator must forward all the updates/new information in a separate Serious Adverse Event Report Form as a follow-up regarding the previously reported SAE. Such information must dwell on recovery or continuation of SAE, diagnosis (if any), therapy details (if any), continuation or discontinuation of that subject from the trial.

Repeated episodes, complications, or progression of the initial SAE should be reported as a follow-up for the original episode, irrespective of the event time.

[figure not shown]
Any new SAE, which is considered as completely unrelated to previously reported one, shall be reported as a new and separate event.

[figure not shown]
The Investigator should answer any questions from LPPV, CRO, or Sponsor regarding SAEs reporting within 24 hours.

For more detailed information, refer to the Quick Reference Guide for Completing the SAE Form.

[figure not shown]
The Investigator should keep the notifications on information delivery to all the recipients in a separate file.

Contact information for SAE reporting

In case of any questions, please contact responsible persons:

Notification of the Investigators and the 6-month line listings

If a serious adverse drug reaction (ADR) is not listed in the reference safety information (e.g., SMPC, Investigator's Brochure), the Sponsor may request for an urgent additional information from the Investigator for reporting to the health authorities.

The Sponsor is entitled to, where applicable, forward notifications for the Investigators and the 6-month line listings of SUSARs (not previously reported) to all the investigators associated with any trial of the same study drug.

The Investigator or CRO (as envisaged in the trial agreement) must submit the notifications for Investigators and the 6-month line listings, if applicable, to Local Ethics Committees (LEC)/Ethics Councils. CRO must submit the notifications for Investigators and the 6-month line listings, if applicable, to the Ethics Council under the Ministry of Health of Russia.

Reporting to health authorities

The Sponsor shall submit all the reports to relevant regulatory authorities within the specified timelines.

Training of investigators

By signing the trial protocol, the Principal Investigator confirms that he/she has passed the training held by CRO and got familiarized with the Sponsor's requirements and his/her responsibilities on reporting the AEs/SAEs and pregnancies as defined in the trial protocol.

8.4 Pregnancy cases

The Investigator must immediately (not later than 24 hours since the receipt of information on pregnancy) inform the Sponsor/LPPV with a copy to a manager responsible for the trial (Sponsor/CRO) as described in Section 8.3.5 on all the pregnancy cases occurred during the trial. Pregnancy reports are registered since the first intake of the study drug only.

The Investigator must exclude the pregnant subject from the trial immediately; this pregnancy should be monitored to determine its termination, including spontaneous or planned abortion, details on delivery and on presence or absence of any development defects, congenital anomalies or complications in infant's mother and/or in a newborn.

If the Investigator becomes aware of pregnancy of the sex partner of a male participant of the trial, which was started with high probability during participation of this man in the trial (i.e., during exposure of the child's father organism to the drug), these pregnancy cases should be also reported after receipt of informed consent from (expecting) mother.

The pregnancy cases should be registered in the Clinical Trial Pregnancy Form. Additional information about pregnancy should be registered in the same form. Moreover, it must include possible relation of any termination of pregnancy to use of the study drug.

Any SAE noted during pregnancy should be reported using SAE Report Form as described in Section 8.3.4.

For more information, see the Clinical Trial Pregnancy Quick Reference Guide; Novartis document.

